6.4.1.1 Criterion for Evaluating PRN Efficacy in ISCC Medication Intervention

A recovery criterion will be computed by the ISCC nurse to evaluate PRN efficacy using raw intrathoracic impedance since it responds dynamically to patient volume status. Computation of recovery criterion requires the difference between raw intrathoracic impedance and the reference impedance. Reference impedance is a component of market approved OptiVol feature in Medtronic devices. Daily values for both raw and reference impedance are included with all device diagnostic transmissions spanning duration of up to 14 months.

The difference between raw and reference impedances on four days is required to compute recovery criterion (RC) – the day CareAlert is received (x_0), and the three PRN intervention days prior to the day RC is evaluated (x_1 , x_2 and x_3), Recovery criterion is then computed according to the following equation and as illustrated in the figure below:

$$RC = 100 * \frac{(x_0 - x_1) + (x_0 - x_2) + (x_0 - x_3)}{x_0}$$

[figure not shown]

Figure 8: Recovery Criteria Illustration

If the value of RC is greater than a threshold value of 70 (i.e. cumulative impedance recovery over the last 3 days is 70% or more from Day 0 of receiving the initial transmission), the intervention is deemed to be successful. If the value of RC is less than or equal to 70, the intervention is deemed to be not a success and appropriate follow-up action (i.e. second PRN or notification to the investigator) is taken.

6.4.1.2 ISCCC Timeframe for Patient Contact to Initiate Intervention

If the ISCC nurse is unable to contact the patient during the first attempt for initiation of first or second rounds of PRN, the following schedule will be used to establish subject contact:

For initiating a first round of PRN: The ISCC nurse will make 1 attempt per day, for a total of 8 subsequent attempts to establish the contact (including weekends). If the ISCC nurse is unable to establish subject contact, a notification will be sent to the investigator. The day of successful subject contact will then be the first day of the medication intervention.

For initiating the second round PRN (or for any medication surveillance on days 8, 12, and 16 post initiation of the first day of medication intervention): The ISCC nurse will make 1 attempt per day of any CareLink transmission to establish subject contact. If unable to establish contact, an 'Exception Report' will be sent to the investigator with continued monitoring per the protocol (see Appendix B: ISCC Reports to Physician for an example of this report).

6.4.2 Investigator Executed Chronic Medication Intervention

The investigator will be responsible for performing the re-evaluation of the subject's chronic medications or HF treatment. Any changes in baseline medications will need to be reported to the ISCC. If no changes were made, rationale as to why changes were not made will need to be provided. In absence of an investigator intervention or documented rationale, lack of intervention by the investigator will be considered a protocol deviation. To aid the investigator in making such changes, a summary of the subject's heart failure related medications at baseline along with guideline recommended doses for these medications will be provided to the investigator as part of the notification (see Appendix B: ISCC Reports to Physician for an example of this report).

6.5 F) Ensuring Subject Safety

6.5.1 Criterion for not initiating or continuing with a PRN Intervention

At the time of subject contact, (following the CareLink transmission and subject having been stratified as High risk), the ISCC nurse will make sure that the subject is not hypotensive based on the blood pressure measurement for the day of contact. If the subject has not yet transmitted the blood pressure measurement for the day of contact, the nurse will instruct the subject to obtain blood pressure measurement while on the phone. If the subject's systolic blood pressure is below 85 mmHG with associated hypotensive symptoms, the intervention will not be initiated. Additionally in the instance that the subject is unable or unwilling to provide a blood pressure measurement, the subject will be assessed for potential hypotensive symptoms – if positively reported, the medication intervention will not be initiated. ISCC will send an 'Interim Patient Report' to the subject's investigator noting the reason for not initiating PRN intervention. Subject's investigator will be required to further evaluate the subject, take necessary actions, and document them in eCRFs.

To ensure subject safety while a PRN intervention is underway, the subject's will be asked to provide a blood pressure and weight daily. If a predefined, physician specified, patient specific, safety threshold is crossed for either weight or blood pressure the subject will be

contacted by ISCC nurse. The nurse will telephonically evaluate the subject for symptoms known to suggest that intervention may not be safe (Table 11). If any one of the two symptoms is present, PRN will be stopped and the investigator will be sent an 'Exception Report' to assist with further subject follow-up (see Appendix B: ISCC Reports to Physician for an example of this report). The ISCC nurse will make one attempt to establish the contact with subject to evaluate subject symptoms to potentially stop PRN intervention. If the nurse is unable to establish the subject contact, a report will be sent to the investigator and/or phone call will be made to the site to notify that values were outside threshold(s).

Table 11: Safety Thresholds for Cessation of Medication Intervention (PRN)

PRN Cessation and Safety Threshold(s):			
Hold/Discontinue PRN Diuretic use if telephonically assessed to have met Weight or BP threshold and Symptom(s):			
Weight Loss:	Weight < 150lbs: 3 lbs/2days Weight 151-300lbs: 4 lbs/2 days Weight > 301lbs: 5 lbs/2days	Or	____ lbs/ ____ days (Physician specified range)
OR			
Blood Pressure:	Systolic of < 85 mmHG or a diastolic of <40 mmHg	Or	< ____ / ____ mmHg (Physician specified value)
AND			
Telephonically Assessed Symptom(s):	New lightheadedness when moving from sitting to standing or Muscle cramping or Charlie horses		

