
Awaken during night short of breath? If Yes then, Feel more short of breath lying down?
 
If Yes then, Did you need extra pillows last night?
 
If Yes then, Did you sleep sitting up last night?

Are your ankles or feet more swollen?

Are you coughing more than usual? If Yes then, Is your cough different today?
 
If Yes then, Does lying flat cause coughing?

If the biometric or symptom data are missing from the day of the CareAlert transmission, the day the CareAlert transmission is reviewed, or the subject has provided less than three days of biometric data in the 7 days prior to receiving the CareAlert transmission, the ISCC nurse will contact the subject to assess the presence of HF related symptoms from questions outlined in Table 10. If any of these symptoms are present, the subject will be assigned an overall risk status of 'High' and further evaluation will be performed to assess if medication intervention is warranted (see section 6.3.2 for information on determining warranted intervention). If no weight gain or symptoms are present and the transmission is categorized as 'Medium' the subject status will be monitored remotely by the ISCC after receiving the transmission.

6.3.2 *Determining if Intervention is Warranted*

To ensure that the intervention is warranted, the ISCC nurse will first determine that the subject is not hypotensive per the following criteria. (If the subject is hypotensive a notification in the form of a 'Interim Patient Report' is sent to the site and intervention will not proceed).

- The subject has no signs of hypotension. For the subject to be considered hypotensive, systolic BP < 85 mmHg or diastolic BP <40 mmHg.

The ISCC nurse will also ask the subject a series of questions to ensure the OptiVol crossing is HF related.

- Have you had a CRT-D device change or lead revision?
- Have you been discharged from a hospital within the last 2 days and did you receive intravenous fluids for 1 or more days while in the hospital?
- Are you experiencing chills/shivering, shaking or muscle aches?
- Have you recently been treated for a COPD exacerbation?
- Any changes in baseline diuretic medication in the past 3 weeks?

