6.4.1 ISCC Executed Acute Medication Intervention (PRN and Counseling)

The ISCC facilitated intervention component will consist of providing reinforcement and direction to the subject as to when they are to self-administer up to two rounds of investigator prescribed PRN to the subject per single transmission that warrants action. The investigator prescribed PRN is initiated after ISCC nurse has ensured that subject has been compliant with their baseline medication regimen including diuretic medications. Each round of PRN will be 3 days long. Thus, no more than 6 days of PRN medication will be administered to the subject.

The example scenario in Figure 6 below is an illustration of this ISCC executed intervention. Referring to Figure 6, the day of the transmission is considered Day 0. Since the OptiVol CareAlert transmission is initiated by the device at 5 PM, the nurse will attempt to contact the patient on the following day (includes weekends). Thus, the ISCC nurse will call the subject via phone on Day 1 (1 day post initial transmission), and upon subject contact, guide the subject to take their first round of investigator prescribed diuretic for 3 days if intervention is warranted (Section 6.3.2 above).

The ISCC nurse will notify the subject's investigator using a 'Interim Patient Report' indicating that the first round of PRN has been initiated (see Appendix B: ISCC Reports to Physician for an example of this report).

One Round of Medication Intervention

[figure not shown]

Figure 6: Example Scenario of One Round of Medication Intervention (PRN).

The efficacy of the PRN is evaluated using raw impedance based recovery criterion. (Refer to section 6.4.1.1 and Figure 8 for a detailed description of determining recover criterion.) Recovery criterion is evaluated on Day 4 (when possible) (4 days post initial transmission or 3 days post PRN initiation) and then again on day 8 (when possible) after first PRN. If the recovery criterion is not met on day 4, a second round of PRN is initiated. The ISCC nurse will notify the subject's investigator using a 'Interim Patient Report' indicating that the second round of PRN has been initiated. Figure 7 illustrates this example scenario of 2 rounds of successive PRNs.

Two Rounds of Medication Intervention

[figure not shown]

Figure 7: Example Scenario of Two Rounds of Medication Intervention (PRN).

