6.5.1.2 Safety Monitoring Using External Biometric Data

Outside of the PRN medication intervention window, subject's blood pressure will be monitored for hypotension per nominal safety threshold of a systolic blood pressure of <85 mmHG or a diastolic blood pressure <40 mm Hg or physician specified threshold, if different. If the hypotension criterion is met, subject will be contacted and assessed for presence of two hypotensive symptoms. These hypotensive symptoms will be assessed by asking the following two questions: Are they experiencing new lightheadedness when moving from sitting to standing? And, are they experiencing any cramping or Charlie horses? If any of the two symptoms or both symptoms are present, the subject will be asked to contact their physician. An 'Exception Report' will be sent to the investigator including a note about their patient's safety issue (see Appendix B: ISCC Reports to Physician for an example of this report). The Investigator will be required to review the report and determine if clinical actions are necessary. Actions along with rationale will be documented in the eCRF. If no actions are needed, rationale for that will also be recorded in the eCRF. If the action is updating of HF medications or PRN prescription, updated medication and PRN forms will be sent to ISCC within 24 hours. Lack of completing eCFR in its entirety will be considered a protocol deviation.

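### Protocol 6.5.1 restates the blood-pressure bar to starting a PRN more loosely than 6.3.2: it adds a symptom condition and drops the diastolic limit

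*Protocol*

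**What the plan says.** Four places in the protocol state a low-blood-pressure limit.

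- **6.3.2, deciding whether a PRN is warranted.** "For the subject to be considered hypotensive, systolic BP < 85 mmHg or diastolic BP <40 mmHg". No symptom is required. When the subject is hypotensive, a report "is sent to the site and intervention will not proceed".
- **6.5.1, start check at subject contact.** The paragraph opens with "the ISCC nurse will make sure that the subject is not hypotensive based on the blood pressure measurement for the day of contact". The sentence that gives the actual criterion then reads: "If the subject's systolic blood pressure is below 85 mmHG with associated hypotensive symptoms, the intervention will not be initiated". If no reading can be obtained, reported hypotensive symptoms alone block the start.
- **Table 11 (within 6.5.1), stopping a PRN under way.** "Hold/Discontinue PRN Diuretic use if telephonically assessed to have met Weight" or blood-pressure threshold, together with a symptom. The nominal pressure threshold is "Systolic of < 85 mmHG or a diastolic of <40 mmHg", or a value set by the physician.
- **6.5.1.2, monitoring outside the PRN window.** "systolic blood pressure of <85 mmHG or a diastolic blood pressure <40 mm Hg or physician specified threshold, if different"; symptoms are assessed after the threshold is met.

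Section 6.4.1 ties the first round to 6.3.2: the subject takes the prescribed "diuretic for 3 days if intervention is warranted (Section 6.3.2 above"). The SAP contains no start criterion. Its section 7.1.2 only repeats the 6.5.1.2 monitoring threshold.

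**The concern.** Sections 6.3.2 and 6.5.1 govern one decision: whether the communication-center nurse tells a subject by telephone to begin extra diuretic. The 6.5.1 sentence stands under a heading that presents it as the criterion for not initiating, so a reader could take it as the complete start rule. Read that way, it lets a PRN begin in subjects whom 6.3.2 would refer back to the site.

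What is at stake is mainly patient safety. The sentence sets the pre-dose check before remote diuretic up-titration, in a study for which Protocol section 14 rules out a data monitoring committee. There is a possible secondary effect. Both primary analyses include subjects who received the intervention, so inconsistent start decisions would change which episodes are analyzed.

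**Working it through.** There is no figure in the plan to reproduce. The check compares the rules as logic.

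**Inputs.** S = systolic <85 mmHg; D = diastolic <40 mmHg; Y = hypotensive symptoms. I assume Y means the same symptoms in 6.5.1 as in Table 11 (new lightheadedness on standing, or cramping), that a reading is available, and that Table 11 is at its nominal pressure threshold with its weight-loss criterion not in play.

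**Rules.**
- 6.3.2 bars the start if S or D.
- The 6.5.1 sentence bars the start if S and Y.
- Table 11 (pressure route) holds a PRN under way if (S or D) and Y.

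**All 2 × 2 × 2 = 8 combinations.**

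| S | D | Y | 6.3.2 bars | 6.5.1 sentence bars | Table 11 holds |
|---|---|---|---|---|---|
| no | no | no | no | no | no |
| no | no | yes | no | no | no |
| no | yes | no | **yes** | **no** | no |
| no | yes | yes | **yes** | **no** | **yes** |
| yes | no | no | **yes** | **no** | no |
| yes | no | yes | yes | yes | yes |
| yes | yes | no | **yes** | **no** | no |
| yes | yes | yes | yes | yes | yes |
| | | **Total yes** | **6** | **2** | **3** |

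**Results.**
1. The two start rules differ in 6 − 2 = 4 combinations. None is barred by 6.5.1 only, so 6.3.2 is always the stricter.
2. Two of the four are systolic <85 without symptoms (for example 82/50). The symptom condition causes these.
3. The other two are diastolic <40 with systolic at or above 85 (for example 95/38, with or without symptoms). Here the missing diastolic limit is enough on its own.
4. The 6.5.1 sentence also falls short of the stopping rule in its own section. Table 11 holds in 3 combinations and the sentence covers 2 of them. It misses 95/38 with new lightheadedness: the sentence does not bar starting, yet the nominal Table 11 rule would hold the PRN.
5. Of the four protocol statements of the limit, three (6.3.2, Table 11, 6.5.1.2) include diastolic <40. Only the 6.5.1 start sentence omits it.

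**Which rule was intended.** The opening of 6.5.1 asks for a judgment from the blood-pressure reading, which fits 6.3.2. The symptom condition resembles Table 11 and 6.5.1.2, but those govern stopping and off-treatment monitoring. If the authors did mean a symptom-based start rule, the 6.5.1 sentence would still lack the diastolic limit and 6.3.2 would also need changing. The text needs correcting on either reading.

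**The case against.** The strongest reply is that the rules do not conflict in operation. Section 6.3.2 is a gate, 6.4.1 makes the first round conditional on it, and the 6.5.1 sentence names one situation that blocks a start without claiming to be the only one. The opening of 6.5.1 uses a term that 6.3.2 has already defined. A nurse who follows the whole protocol therefore starts nobody in the four differing combinations.

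Most of this stands, and it limits the likely harm. It does not remove the defect. Neither section refers to the other, nothing says that the stricter rule prevails, and an explicit symptom condition invites the inference that symptom-free subjects may start. The nurses' guided workflow (Protocol 3.2) might settle the matter, but it is not in the documents.

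Three narrower objections:
- **Unweighted logical combinations say nothing about how many patients are affected.** This is correct.
- **Fixed 85/40 limits ignore subject-specific thresholds.** Table 12 and section 7.8 tie the thresholds set at baseline to PRN cessation, and 6.3.2 already uses fixed limits for starting. This does not count against aligning 6.5.1 with 6.3.2.
- **Round two is left open.** This has some force. Section 6.4.1 points to 6.3.2 for the first round, but its second-round sentence has no such pointer.

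**Conclusion.** The point holds. The 6.5.1 start sentence departs from 6.3.2 in two ways, and both make it more permissive: 4 of 8 rule combinations differ, all in that direction. It also fails to match Table 11 in its own section.

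Calling it a misstatement rests on taking 6.3.2 as the intended start rule. The opening of 6.5.1 and the pointer in 6.4.1 support that, but the documents do not say so outright. Harm would require a nurse to act on the 6.5.1 sentence without 6.3.2, which those same two texts make less likely. The documents do not say how often such readings occur, so the effect on the effectiveness and safety rates cannot be sized. It is probably small. This should be fixed for patient safety and for a single consistent start rule; no threat to either primary analysis is shown.

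**What to change.** Replace the 6.5.1 sentence with: *If systolic blood pressure is <85 mmHg or diastolic is <40 mmHg, with or without symptoms, the intervention will not be initiated (see 6.3.2).* Add a cross-reference to 6.5.1 in 6.3.2. Keep the existing symptoms-only rule for subjects with no reading, and leave Table 11 unchanged. While editing, the sponsor could say whether the same check applies before a second round.

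The clinical price is that symptom-free subjects with low pressure get no PRN and are referred to the investigator, which 6.3.2 already requires. Endpoints, analysis and sample size are unaffected. Protocol section 4 requires sponsor approval and IRB approval at each center for any revision, so the change can go in with the next one. The nurses' workflow should be checked against the amended sentence at the same time.

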6.5.1.1 Criteria to Perform Blood work and Related Actions

Blood work will be performed by the site if PRN intervention is stopped anytime because of safety concern. Blood work will also be performed if 2 rounds PRNs are completed irrespective of whether the intervention is deemed success or failure after 2 PRNs. The participating site will be notified by ISCC via Interim Patient Report to notify site to perform blood work for the subject. Blood work and evaluation by the participating investigator will be required to be performed within 7 days of the notification and associated eCRF will need to be completed. Blood work, at a minimum, should include creatinine (needed to estimate eGFR) and electrolytes (K+ and Na+). Investigators will be required to record creatinine,

eGFR, K⁺ and Na⁺ in the eCFR. Any actions taken along with the rationale will also be recorded in the eCFR. If the action is updating of HF medications or PRN prescription, the updated medication and PRN forms will be sent to ISCC within 24 hours. Lack of completing this blood work eCFR in its entirety will be considered a deviation.

6.5.1.2 Safety Monitoring Using External Biometric Data

Outside of the PRN medication intervention window, subject's blood pressure will be monitored for hypotension per nominal safety threshold of a systolic blood pressure of <85 mmHG or a diastolic blood pressure <40 mm Hg or physician specified threshold, if different. If the hypotension criterion is met, subject will be contacted and assessed for presence of two hypotensive symptoms. These hypotensive symptoms will be assessed by asking the following two questions: Are they experiencing new lightheadedness when moving from sitting to standing? And, are they experiencing any cramping or Charlie horses? If any of the two symptoms or both symptoms are present, the subject will be asked to contact their physician. An 'Exception Report' will be sent to the investigator including a note about their patient's safety issue (see Appendix B: ISCC Reports to Physician for an example of this report). The Investigator will be required to review the report and determine if clinical actions are necessary. Actions along with rationale will be documented in the eCRF. If no actions are needed, rationale for that will also be recorded in the eCRF. If the action is updating of HF medications or PRN prescription, updated medication and PRN forms will be sent to ISCC within 24 hours. Lack of completing eCFR in its entirety will be considered a protocol deviation.

6.6 H) Exit Visit

Please refer to section 7.14 for details on exiting procedures.

7 SITE RELATED PROCEDURES

Prior to performing study related procedures, all sites must have IRB and associated regulatory authority approval (if applicable) as well as documentation from Medtronic of site readiness.

7.1 Investigator/Investigation site selection

All clinical investigators managing the subject's heart failure must be qualified practitioners and experienced in the diagnosis and treatment of subjects with heart failure.

The role of the investigator is to implement and manage the day-to-day conduct of the clinical investigation as well as ensure data integrity and the rights, safety and well-being of the subjects involved in the clinical investigation.

The investigator shall:

- Be qualified by education, training, and relevant experience appropriate to the use of the product and associated procedures as defined below:

- Diagnoses/Treats patients with HF
- Willing to partner with ancillary service provider hosted at Medtronic to guide medication intervention for acute HF volume management under physician standing order.
- Center is willing to coordinate with their CareLink Manager to transfer patient into the Virtual CareLink-HF clinic for the duration of the study. (The patient will still be part of the CareLink EP).
- Disclose potential conflicts of interest, including financial, that interfere with the conduct of the clinical investigation or interpretation of results

The investigator shall be able to demonstrate that the proposed investigational site has adequate resources, including, as applicable, facilities, laboratories, equipment, and a qualified trial site team. Center personnel training will be completed prior to participation in this clinical study.

The investigator shall have access to an adequate number of patients with the following:

- Center should have a pool of patients with implanted Medtronic CRT-D devices with wireless telemetry.
- Center should have a pool of patients with NYHA Class II and/or Class III Heart Failure.

